22.4.2 Investigator's Assessment of Clinical Response at PTE Efficacy Variable

This is defined as Investigator's Assessment of Clinical Response at the PTE visit with outcomes of Clinical Success, Clinical Failure and Indeterminate (defined in [Section 17.4.3](#)) in the mITT population and Clinical Success and Clinical Failure in the CE population. Subjects with a response of Clinical Failure at EOT will be defined as a Clinical Failure at PTE. An Indeterminate Response is included in the denominator for the calculation of the percentage of subjects with a Clinical Success in the mITT population and thus, is essentially considered a Clinical Failure for the purpose of the primary analysis for the EMA.

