5.2.2.1.1 EOT Visit

At the EOT visit (on the day of or within 2 days following the last dose of test article), the investigator will indicate the clinical status of the infection under study as detailed below.

Clinical Success at the EOT assessment will be defined as meeting the following:

- The subject is alive
- The infection is sufficiently resolved such that further antibacterial therapy is not needed. These subjects may have some residual changes related to infection requiring ancillary (ie, non-antibiotic) treatment, eg, bandages on a healing wound, debridement of uninfected tissue (ie, necrotic)

Clinical Failure will be defined as meeting any of the criteria below:

- Investigator discontinued test article and indicated that the infection had responded inadequately such that alternative (rescue) antibacterial therapy was needed
- The subject received antibacterial therapy that may be effective for the infection under study for a different infection from the one under study
- The subject developed an AE that required discontinuation of test article prior to completion of the planned test article regimen and alternative (rescue) antibacterial therapy was needed
- Unplanned major surgical intervention (ie, procedures that would not normally be performed at the bedside) for the infection under study
- The subject died before evaluation

- Other specified reason as indicated on the eCRF.

Indeterminate The clinical response to test article could not be adequately inferred:

- The subject was not seen for EOT assessment because they withdrew consent, were lost to follow-up, or other specified reason
- Other specified reason

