6.1.5.3 Concomitant Antibiotic Therapy

Subjects who receive any systemic concomitant antibiotic therapy from the first dose of test article through the EOT visit and through the PTE visit with a spectrum of activity against the known or potential Gram-positive infecting pathogen(s) responsible for the infection under study will be excluded from the CE-EOT and CE-PTE populations, respectively, unless the subject receives the antibiotic therapy for treatment of the ABSSSI due to insufficient therapeutic effect of the test article.

Subjects who receive a systemic concomitant antibiotic that is not effective against the Gram-positive baseline pathogen, or if no Gram-positive pathogen is isolated and the antibiotic does not have Gram-positive activity, will be included in the CE-EOT and CE-PTE populations.

In addition, subjects who have any topical antibacterial agent applied to the infection site (except for antibiotic/antiseptic-coated dressing applied to the clean postsurgical wound) with a spectrum

that is active against the known or potential infecting pathogen(s) responsible for the infection under study from the first dose of test article through the EOT or PTE visits, will be excluded from the CE-EOT and CE-PTE populations, respectively.

Antimicrobials that will not interfere with the course of the ABSSSI are allowed and do not affect inclusion in the CE populations, eg, metronidazole, norfloxacin, nalidixic acid, piperacillin sodium, oral vancomycin, antifungals, antivirals or topical antibiotics used for decontamination or in places other than the primary lesion.

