6.1.5.4 Concomitant Surgical Procedures

Subjects who receive an unplanned major surgical procedure for the infection under study (ie, procedures that would not normally be performed at the bedside, such as amputation or major incision and drainage performed in an operating room) will be defined as a clinical failure for the clinical response at the EOT and PTE Visits and thus, will be included in the CE populations.

Minor bedside procedures such as debridement, aspiration puncture, excision with or without skin grafting and wound cleaning/lavage will generally be acceptable and will not exclude a subject from the CE populations. All other surgical procedures performed after the first dose of test article will be reviewed by the Sponsor to determine whether the procedure potentially confounds the outcome and whether the subject should be excluded from either the CE-EOT or CE-PTE populations.

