6.1.5.5 Test Article Therapy

Subjects must meet all of the following to be included in the CE populations:

- Received test article and the correct test article based on the randomization assignment
- Study personnel involved in the assessment of efficacy remained blinded to study treatment, unless a treatment limiting adverse event occurred which required emergency unblinding.
- Subject was at least 80% compliant with the dosing regimen.
- Evaluable failure: The subject received at least 2 doses of active test article (omadacycline group) or at least 4 doses of active test article (linezolid group) and the investigator classifies the subject as a Clinical Failure at the EOT Visit (CE-EOT population) or the overall Clinical Response (based on the investigator's assessment) at the PTE Visit (CE-PTE population) is Clinical Failure.
- Evaluable success: The subject received at least 3 doses of active test article (omadacycline group) or at least 6 doses of active test article (linezolid group) and the investigator classifies the subject as a Clinical Success at the EOT Visit (CE-EOT population) or the overall Clinical Response (based on the investigator's assessment) at the PTE Visit (CE-PTE population) is Clinical Success.

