9.3 Treatment Compliance and Exposure

Exposure summary by treatment group will be presented for the Safety, mITT, and CE-PTE populations. The distribution of subjects by the total number of days on therapy (1 to 3, 4 to 6, 7 to 10, 11 to 12, 13 to 14 and > 14 days) will be presented as will descriptive statistics for the total number of days on therapy.

Treatment compliance is defined as the number of active tablets actually received divided by the number of active tablets expected ($\times 100$) over the time period defined by the first and last dose date. The last dose date is the last day the subject is expected to receive test article based on the length of therapy determined by the Investigator or the actual last date the subject took test article, if s/he prematurely discontinued test article due to treatment failure or an adverse event. Dose 2 can be missed per protocol if it cannot be taken a minimum of 8 hours after Dose 1 and a minimum of 8 hours before the expected time of Dose 3. Descriptive statistics for treatment

compliance and the number and percentage of subjects at least 80% compliant will be presented by treatment group for the mITT and Safety populations.

A summary of compliance with the pre- and post-dose fasting requirements will also be provided. The percent fasting compliance will be determined based on the total doses taken where fasting is required. The percentage of subjects who were < 50%, 50% to < 80%, and 80% to 100% compliance with the pre-dose and post-dose fasting requirements will be summarized for the mITT and Safety populations.

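### SAP 6.1.5.3 drops from the CE populations subjects who stop for an adverse event and need rescue, although the plan defines them as Clinical Failures; comparable stoppers who succeed are kept

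*SAP*

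**What the plan says.** **Failure definition.** Protocol 17.4.2 and SAP 5.2.2.1.1 list as a Clinical Failure at EOT: "The subject developed an AE that required discontinuation of test article prior to completion of the planned test article regimen and alternative (rescue) antibacterial therapy" being needed. This is a separate criterion from inadequate response. Protocol 22.4.2 carries it forward: "Subjects with a response of Clinical Failure at EOT will be defined as a Clinical Failure at PTE". SAP Table 2 does the same.

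**CE rule on concomitant antibiotics.** SAP 6.1.5.3 removes subjects given a systemic antibiotic active against the known or potential Gram-positive pathogen, through EOT for CE-EOT and through PTE for CE-PTE, "unless the subject receives the antibiotic therapy for treatment of the ABSSSI due to insufficient therapeutic effect of the test article". No other exception is given for active systemic agents.

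**Neighbouring CE rules.**
- SAP 6.1.5.4: subjects with unplanned major surgery for the study infection are failures, "and thus, will be included in the CE populations".
- SAP 6.1.5.5: "Subjects must meet all of the following to be included in the CE populations". The list includes correct test article, 80% compliance and preserved blinding, "unless a treatment limiting adverse event occurred which required emergency unblinding". An evaluable failure needs 2 omadacycline or 4 linezolid active doses; an evaluable success needs 3 or 6.
- SAP 9.3: compliance is counted to the actual last dose "if s/he prematurely discontinued test article due to treatment failure or an adverse event".

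**Role of CE.** In this SAP (10.3), the CE-PTE interval is descriptive. Under protocol 22.4.3, PTE response in mITT and CE is co-primary for the EMA, and non-inferiority must be shown in both.

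**The concern.** An evaluable population usually removes subjects whose other antibiotics could turn a failure into an apparent success. That reason does not apply here: the need for rescue is itself the failure event, so the rescue drug cannot make the subject a success. The SAP already accepts this logic for rescue after insufficient effect and for major surgery.

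The result is selection on outcome among AE stoppers. Two subjects with the same exposure and the same reason for stopping are treated differently: the one who does well counts as a CE success, and the one who needs active systemic rescue leaves the denominator. One of the plan's failure categories can then almost never appear in CE. CE success rates are too high in both arms, and the CE difference is distorted if these failures are unevenly distributed. This matters most where CE carries inferential weight, which is the EMA analysis.

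**Working it through.** **1. Which subjects are affected.** Take an omadacycline subject who stops for an AE after Day 3.
- Tablets taken: 3 + 3 + 2 = 8. Tablets expected up to the actual last dose (SAP 9.3): 8. Compliance is 100%. Against an assumed 10-day course it would be 8/(3 + 3 + 8 × 2) = 8/22 = 36%.
- Active doses: 3, which meets both minimums in 6.1.5.5.
- No rescue, judged a success: in CE if the other criteria are met.
- Systemic Gram-positive-active rescue because of the AE: Clinical Failure, excluded by 6.1.5.3. The evaluable-failure item in 6.1.5.5 is one cumulative condition and does not override 6.1.5.3.

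Four limits apply. The rescue must be systemic and Gram-positive-active. A subject whose rescue is also recorded as given for insufficient effect is kept. Successes with fewer than 3 or 6 active doses are excluded too. Rescue begun after the EOT visit affects only CE-PTE.

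**2. The plan's own CE figure.** Inputs from SAP 5.1.1: 564 CE subjects (282 per arm), 90% success, margin 0.10, 1-sided alpha 0.025. Farrington-Manning power = Φ{[(p1 - p2 + 0.10)√n - 1.96 s0]/s1}, where s0 is computed from the restricted null estimates and s1 = √(2 × 0.9 × 0.1). Result: 96.9%; the plan states 97%. Nothing here disputes that figure.

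**3. Effect of returning the excluded failures.** The documents do not give the number of AE-plus-rescue subjects, so the counts are assumptions. Base case: 0.90 × 282 ≈ 254 successes per arm. Returning k failures to an arm makes its rate 254/(282 + k). Limits are from the unstratified Miettinen-Nurminen method of SAP 10.1.

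Two rows use AE-discontinuation rates from protocol 9.1 and assume that every AE stopper needed rescue and was otherwise evaluable:
- Phase 2 study, 0.9% vs 1.9%: 0.009 × 282 = 2.5 and 0.019 × 282 = 5.4, rounded to 3 and 5.
- Completed Phase 3 iv/oral ABSSSI study, 1.9% vs 2.2%: 5.4 and 0.022 × 282 = 6.2, rounded to 5 and 6.

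| Returned failures (omadacycline/linezolid) | Success rates, % | Difference, points | 95% lower limit, points |
|---|---|---|---|
| 0/0 (as planned) | 90.1 / 90.1 | 0.0 | -5.0 |
| 3/5 (Phase 2 rates) | 89.1 / 88.5 | +0.6 | -4.6 |
| 5/6 (Phase 3 rates) | 88.5 / 88.2 | +0.3 | -5.0 |
| 3/3 (assumed) | 89.1 / 89.1 | 0.0 | -5.2 |
| 6/3 (assumed) | 88.2 / 89.1 | -0.9 | -6.2 |
| 9/3 (assumed) | 87.3 / 89.1 | -1.8 | -7.2 |
| 12/3 (assumed) | 86.4 / 89.1 | -2.7 | about -8.2 |

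At the prior rates, CE success is overstated by about 0.9 points (90.07 - 89.12) to 1.9 points (90.07 - 88.19) per arm. The difference moves by at most 0.6 points, in omadacycline's favour. The 9/3 and 12/3 rows need 9/291 = 3.1% and 12/294 = 4.1% of omadacycline subjects to stop for an AE and need rescue, above the 1.9% stopping for any treatment-emergent AE in the earlier Phase 3 study.

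**The case against.** **Direction.** A reader might infer that the rule pushes CE towards non-inferiority, because protocol 9.1 reports more gastrointestinal events at oral doses of 400 mg or more. The documents do not support that. The statement concerns early studies, and the protocol adds that formulation may have contributed. Protocol 15.3 reports similar tolerability for 300 mg and 450 mg once daily. Both by-arm AE-discontinuation rates in protocol 9.1 are lower for omadacycline. Those studies allowed iv treatment, so the direction for oral-only treatment is unknown.

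**Intent.** A reader might also infer that 6.1.5.5 and 9.3 were written to keep these subjects. That goes too far: the unblinding exemption covers successes and failures alike, and the compliance rule also covers treatment failure. The surgery contrast is limited too, since that surgery is for the study infection and lies close to insufficient effect. What remains is that 6.1.5.4 keeps subjects in CE because they are failures, and 6.1.5.3 does not do so here.

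**Visibility.** These subjects remain failures in mITT, the EMA claim needs both populations, and the SAP tabulates reasons for exclusion (9.1) and TEAEs leading to discontinuation (11.1). This stands: the failures are not hidden from the trial, and CE alone cannot carry the EMA claim. It does not make the CE estimate right.

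**Consistency.** The same sentence drops failures given an active antibiotic for a different infection. If one exclusion is wrong, why not both? This has some force. The distinction is that the other infection's antibiotic was not prompted by the study infection or by intolerance of test article, so the usual confounding argument applies to it.

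**Conclusion.** The inconsistency is real on the text. Subjects who stop for an AE and receive active systemic rescue for the ABSSSI are Clinical Failures by definition but are excluded from CE, while otherwise evaluable AE stoppers who succeed are kept. CE success is inflated, by roughly 1 to 2 points per arm if the prior AE-discontinuation rates hold and every such stopper needed rescue.

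The bias in the between-arm difference is of unknown sign and probably small. Under the prior rates the illustrative lower limit stays between -4.6 and -5.0, and none of the scenarios shown reaches -10. It worsens materially only if AE-plus-rescue failures are clearly more frequent on omadacycline. These figures rest on 254/282 successes per arm, assumed counts and the unstratified method; the EMA analysis is to be stratified.

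The primary mITT Early Clinical Response analysis is untouched. In this SAP the consequence is limited to descriptive CE results. Whether the EMA co-primary CE analysis shares the rule cannot be judged without its SAP.

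**What to change.** Before unblinding:

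1. Extend the exception in SAP 6.1.5.3 to systemic antibiotic therapy given for the ABSSSI after test article was discontinued for an AE. State that these subjects, already Clinical Failures under 5.2.2.1, are evaluable failures if they meet the 6.1.5.5 dose minimum and the other CE criteria.
2. Report CE-PTE with and without these subjects as a sensitivity analysis.
3. Check the EMA SAP for the same rule and align it.

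The exclusion for antibiotics given for a different infection can stay. If the sponsor prefers to keep AE-plus-rescue failures out of CE, the SAP should say so and give the reason; the two-way report then becomes more important.

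The cost is a sentence in the SAP and one extra table. No new data are needed, because the reason for stopping and the antibiotic records are already collected, and subject management does not change. The downside is a slightly lower CE success rate and a CE set that includes intolerance failures, in line with the plan's own failure definition.

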13.2 Permitted Treatments

All other treatments not specified as prohibited are permitted during the study. A single dose of a short-acting potentially effective systemic antibacterial agent (see list in [Appendix 1](#)) administered within the 72 hours prior to randomization will be allowed for up to 25% of randomized subjects. Subjects requiring additional or alternative antibacterial therapy for the ABSSSI will be judged as Clinical Failures and test article will be discontinued. Further treatment for their infection is at the discretion of the investigator or the subject's health care provider and will be considered as a concomitant medication.

Subjects should be encouraged to contact site personnel before starting any new treatment.

For all treatments received by the subject during the study, relevant information must be recorded on the subject's eCRF.

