5.2.2.1.2 PTE Visit

At the PTE Visit (7 to 14 days after the subject's last day of study therapy) the investigator will indicate one of the following outcomes relating to the primary infection under study:

Clinical Success at the Post Therapy Evaluation assessment will be defined as meeting the following:

- The subject is alive
- The infection is sufficiently resolved such that further antibacterial therapy is not needed. These subjects may have some residual changes related to infection requiring ancillary (ie, non-antibiotic) treatment, eg, bandages on a healing wound, debridement of uninfected tissue (ie, necrotic)

Clinical Failure will be defined as meeting any of the criteria below:

- The infection required additional treatment with alternative (rescue) antibacterial therapy
- The subject received antibacterial therapy between EOT and PTE that may be effective for the infection under study for a different infection from the one under study
- Unplanned major surgical intervention (ie, procedures that would not normally be performed at the bedside) for the infection under study between EOT and PTE
- The subject died before evaluation
- Other specified reason

Indeterminate The clinical response to test article could not be adequately inferred:

- The subject was not seen for PTE assessment because they withdrew consent, were lost to follow-up, or other specified reason
- Other specified reason

Overall Clinical Response at PTE (based on the investigator's assessment) is determined as follows ([Table 2](#)) from the investigator's assessments at the EOT and PTE Visits:

Table 2. Investigator's Assessment of Clinical Response

EOT Visit	PTE Visit	Overall Assessment of Clinical Response at PTE Visit
Success	Success	Success
Success	Failure	Failure
Success	Indeterminate	Indeterminate
Failure	Success	Failure
Failure	Failure	Failure
Failure	Indeterminate	Failure
Indeterminate	Success	Indeterminate
Indeterminate	Failure	Failure
Indeterminate	Indeterminate	Indeterminate

EOT = end of treatment; PTE = post-therapy evaluation.

For the mITT population, the proportion of mITT subjects with a Clinical Success is defined using the following formula (where the denominator adds to the total number of subjects in the mITT population):

$$\frac{\text{Number of subjects with Clinical Success}}{(\text{Number of subjects with Clinical Success} + \text{Number of subjects with a Clinical Failure} + \text{Number of subjects with an Indeterminate response})}$$

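### SAP 6.1.5.3 keeps Clinical Failures in the CE populations after systemic rescue but drops those whose rescue includes an active topical agent on the lesion

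*SAP*

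**What the plan says.** SAP 6.1.5.3 has two exclusions for antibacterial use during the study.

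- **Systemic agents.** Subjects given an active systemic antibiotic are excluded, "unless the subject receives the antibiotic therapy for treatment of the ABSSSI due to insufficient therapeutic effect of the test article". Failures with systemic rescue therefore stay in CE as failures.
- **Topical agents.** A further exclusion covers "subjects who have any topical antibacterial agent applied to the infection site (except for antibiotic/antiseptic-coated dressing applied to the clean postsurgical wound") if the agent is active against the known or potential pathogen. Such subjects, when the use falls "from the first dose of test article through the EOT or PTE visits, will be excluded from the CE-EOT and CE-PTE populations, respectively". The only other relief, in the last paragraph of the section, is for "topical antibiotics used for decontamination or in places other than the primary lesion". Treatment failure is not mentioned.

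The failure definitions set no limit on route. SAP 5.2.2.1.2 counts a subject as a failure at PTE if "The infection required additional treatment with alternative (rescue) antibacterial therapy". Protocol 13.2 states: "Subjects requiring additional or alternative antibacterial therapy for the ABSSSI will be judged as Clinical Failures". It adds: "Further treatment for their infection is at the discretion of the investigator" or of the subject's health care provider.

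SAP 6.1.5.4 handles unplanned major surgery the other way. Those subjects are defined as failures "and thus, will be included in the CE populations".

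**The concern.** Elsewhere the CE rules keep a subject whose extra intervention was a consequence of failing. Systemic rescue and unplanned major surgery are both handled so, and SAP 6.1.5.6 waives the PTE visit window for subjects who had already failed at EOT. Topical rescue is the exception, and no reason is given.

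A Clinical Success by definition needs no further antibacterial therapy, so deletion triggered by rescue can fall only on failures. Under SAP Table 2, a failure at EOT remains an overall failure at PTE whatever happens later. A topical agent started after that point cannot alter the outcome, yet it removes the subject from CE-PTE. Two subjects with the same outcome, one given systemic rescue alone and the other systemic rescue plus a topical agent on the lesion, are treated differently.

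At stake are the CE and ME success rates and, where failures are deleted in similar proportion in both arms, a treatment difference pulled toward zero. In a non-inferiority comparison that is the anti-conservative direction.

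**Working it through.** **Inputs from the documents.** CE size 564, so 282 per arm at 1:1; CE success 90%; margin 10%; one-sided alpha 0.025 (SAP 5.1.1).

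**Plan's own figures.** 0.80 × 704 = 563.2, or 281.6 per arm; rounded up to 282 this gives 564. Farrington-Manning power is Φ[(Δ√n − 1.96·s0)/s1]. The restricted null rates are 0.8313 and 0.9313, so s0 = √(0.8313×0.1687 + 0.9313×0.0687) = 0.452, and s1 = √(2×0.9×0.1) = 0.424. Then (0.10×√282 − 1.96×0.452)/0.424 = 1.87, which gives 96.9% against the stated 97%.

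**Who is caught.** The agent must be on the infection site, be active, and fall in the window. Use by the EOT visit removes the subject from CE-EOT and CE-PTE. Use only after EOT removes the subject from CE-PTE alone. The ME populations follow, because SAP 6.1.6 makes them subsets of CE.

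**Effect per deletion.** With 254 successes in 282:

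- none deleted: 254/282 = 90.07%
- one failure deleted: 254/281 = 90.39%, a rise of about 0.3 points
- three deleted: 254/279 = 91.0%
- six deleted: 254/276 = 92.0%

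**Effect on the comparison** (unstratified Miettinen-Nurminen lower 95% limit):

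| Omadacycline | Linezolid | Difference | Lower limit |
|---|---|---|---|
| 254/282 | 254/282 | 0 | −5.04% |
| 254/276 | 254/276 | 0 | −4.65% |
| 254/276 | 254/282 | +2.0 | −2.9% |
| 240/282 | 254/282 | −5.0 | −10.52% |
| 240/280 | 254/282 | −4.4 | −9.87% |

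Equal rates with equal deletion leave the difference at zero and only narrow the interval. The last two rows are a constructed borderline case in which deleting two omadacycline failures moves the limit across −10%.

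**Equal share of failures deleted in both arms.** If a share t is deleted, the success rate becomes p/[p + (1−p)(1−t)]. The documents give no value for t; 5% to 20% is assumed for illustration.

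- At 90%: 0.90/0.995 = 90.5% (t = 5%) to 0.90/0.98 = 91.8% (t = 20%). Of about 56 failures (10% of 564), 3 to 11 are lost.
- True 86% vs 94% (−8 points): 86.6% vs 94.3% = −7.7, to 88.5% vs 95.1% = −6.7.
- True 80% vs 90% (−10 points): −9.6 to −8.5. With the standard error at the reduced sample sizes, a CE-only non-inferiority test would reject with probability Φ(0.121 − 1.96) = 3.3% at t = 5%, Φ(0.250 − 1.96) = 4.4% at 10%, and Φ(0.534 − 1.96) = 7.7% at 20%, against a nominal 2.5%.

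**Unequal shares.** With 80% vs 90%, t = 0 for omadacycline and 20% for linezolid, the difference becomes 80.0 − 91.8 = −11.8. The bias then runs the other way.

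**The case against.** **The protocol bars the trigger.** Protocol 13.1 prohibits active topical agents on the infection site through PTE. Its bullet on systemic agents has a rescue exception and its topical bullet has none. Protocol 13.2.2 also keeps specific topical antibacterials out of local site care. On this view the SAP merely removes users of a prohibited treatment from an evaluable population. This stands as a limit on frequency, which could be zero. It does not remove the asymmetry: 13.2 leaves care after failure to investigators and outside providers, and a prohibited agent given after failure still deletes a failure.

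**The size is assumed.** Nothing in the documents supports 5% to 20%. A reader might infer that CE success is inflated by a known amount, but only the effect per deletion can be stated.

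**Shrinkage is conditional.** A reader might infer that any true difference always moves toward zero. That needs similar shares in both arms, as the −11.8 example shows.

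**No decision in this SAP carries the 3.3% to 7.7% error.** The FDA primary analysis is Early Clinical Response in mITT, and SAP 10.3 makes CE-PTE descriptive. For the EMA, non-inferiority must be shown in both mITT and CE (protocol 22.4.3), and mITT keeps these subjects as failures. If the true mITT difference is also at the margin, the joint error cannot exceed the 2.5% of the mITT test. The EMA SAP is not among the documents and may define CE differently. All of this stands.

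**Deletions would be visible.** SAP 9.1 tabulates reasons for exclusion, SAP 13.2 summarises topical use with reasons, and the Evaluability Review Team reviews CE membership blinded (SAP 6.2). This helps detection, but no rule lets the team override the exclusion.

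**Conclusion.** The concern holds as an inconsistency in the CE rules that makes exclusion depend on outcome. A Clinical Failure whose rescue includes an active topical agent on the lesion is removed from CE and ME because of treatment given after failing; comparable failures with systemic rescue or major surgery are kept. Each deletion adds about 0.3 points to that arm's CE success rate at the planned 90% and 282 per arm. A true difference shrinks toward zero only if the share of failures deleted is similar in both arms.

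The number affected is unknown and may be small. The CE-only error figures are illustrative and rest on an assumed share. The documents do not support reading this as a threat to the FDA primary conclusion, or as a demonstrated inflation of the EMA error rate. Its weight depends on whether the EMA SAP uses the same rule. It is worth correcting because the repair is cheap and can be made before unblinding.

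**What to change.** Add an exemption to the topical paragraph of SAP 6.1.5.3, for example: *unless the topical agent was used against the ABSSSI because the test article was not sufficiently effective, or was begun after the subject had already been classified as a Clinical Failure; such use does not by itself exclude the subject, who is included as a Clinical Failure if all other CE criteria are met.* The closing condition is needed so that the clause does not override the dose, compliance and visit criteria in SAP 6.1.5.5 and 6.1.5.6.

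Confirm that the EMA SAP uses the same rule. The topical prohibition in protocol 13.1 and the discretion after failure in protocol 13.2 must also be reconciled; which should prevail is for the clinical team.

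The cost is one clause and one programming condition. SAP 13.2 already plans to summarise topical antibacterial use with its reasons, so the information needed should be at hand. The reported CE success rate could be slightly lower.
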